9.7. LEVEL OF SIGNIFICANCE

P-values will be descriptive in nature.

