4.2. General Statistical Methods and Data Handling

4.2.1. General Methods

All output will be incorporated into Microsoft Excel or Word files, sorted and labeled according to the International Conference on Harmonisation (ICH) recommendations, and formatted to the appropriate page size(s).

Tabulations will be produced for appropriate demographic, baseline, efficacy, and safety parameters. Baseline is considered to be the last assessment prior to first dose. For categorical variables, summary tabulations of the number and percentage within each category (with a category for missing data) of the parameter will be presented. For continuous variables, the mean, median, standard deviation, minimum and maximum values will be presented.

Formal statistical hypothesis testing will be performed on the VAS scores, Total MGD score, eyelid margin vascularity, LGS grade, conjunctival hyperemia, Schirmer score, TBUT, FCS, and OSDI with all tests conducted at the 2-sided, 0.05 level of significance. Summary statistics will be presented, as well as confidence intervals on selected parameters, as described in the sections below.

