4.2.5. Multiple Comparisons/Multiplicity

Multiplicity is not of concern for this study.

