4.4. Subject Disposition

Subject disposition will be tabulated by treatment group, including the number screened overall, the number and percent randomized, the number and percent dosed with 0.2% AXR-270 Cream, the number and percent dosed with 2.0% AXR-270 Cream, the number and percent dosed with Vehicle, the

Sponsor:	AxeroVision, Inc.		
Protocol:	AXR201901		
Document Version No.:	1.1	Document Date:	26-OCT-2020

number and percent that completed the treatment, the number and percent that discontinued treatment and the reasons for discontinuation, the number and percent that completed the study, the number and percent that discontinued prior to completing the study and the reasons for discontinuation, and the number in each subject population for analysis.

A summary will be provided for investigator enrollment by country, study center, and investigator name(s) by treatment dose and overall.

A by-subject listing of study completion information, including the reason for premature treatment and/or study discontinuation, if applicable, will be presented.

4.5. **Demographic and Baseline Characteristics**

Baseline and demographic information will be summarized for the FAS, PPS, and SAF using descriptive statistics by treatment group. Medical history will be summarized for the FAS by treatment group, where medical history includes systemic surgical, ocular surgical, systemic non-surgical, and ocular non-surgical history summarized separately by treatment group. No formal statistical comparisons will be performed.

Baseline, demographic, and medical history data will be provided in data listings.

4.6. **Efficacy Evaluation**

Efficacy analysis will be conducted using the FAS and PPS as outlined below.

All efficacy endpoints are exploratory in nature. The following endpoints will be considered to assess the efficacy of AXR-270 Cream on the study eye/eyelid.

1. Change from baseline in the following individual subject-reported symptoms using VAS (0-100 point scale) in the AXR-270 Cream (0.2% or 2.0%) arms compared to Vehicle at Day 22:
 - Eye Discomfort
 - Eye Dryness
2. Change from baseline in Investigator-related signs of MGD using individual severity scores in AXR-270 Cream arms compared to Vehicle at Day 22:

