A study eye/eyelid is eligible if Inclusion Criteria #3, Inclusion Criteria #5, and Exclusion Criteria #3 are met for the same eyelid at Visit 1 and Visit 2.

Inclusion Criteria #3: Have a clinical diagnosis of moderate to severe MGD and who meet both of the following criteria, in at least one qualifying eyelid (upper and lower eyelid for each eye will be evaluated independently), at both Visit 1 (Screening) and again in the same eye/eyelid at Visit 2 (Randomization) examinations:

Sponsor:	AxeroVision, Inc.		
Protocol:	AXR201901		
Document Version No.:	1.1	Document Date:	26-OCT-2020

- a) Total MGD Score ≥ 5 and ≤ 14 (the sum of the individual score of 5 central glands on the upper and lower eyelids will be evaluated, each will be scored from 0-3: 0 = clear/slightly yellow, 1 = opaque/yellow, whitish, particulate, 2 = paste, 3 = none/occluded; total score will range from 0-15).
- b) Clinical sign severity score of at least 2 (moderate) on vascularity of the eyelid margin

Inclusion Criteria #5: Meet the following criteria, in both or the same qualifying eye as in Inclusion #3, at both Visit 1 (Screening) and Visit 2 (Randomization) examinations:

- a) tFCS score ≥ 3 and ≤ 14 in the NEI/Industry Workshop scale (0-15)
- b) Schirmer score of >7 mm without topical anesthesia

Exclusion Criteria #3: In the study eyelid, have greater than 4 glands that are not expressible from the 5 upper and/or 5 lower eyelid meibomian glands at both Visit 1 and Visit 2.

Least squares means for each treatment group and for the differences between 0.2% AXR-270 Cream and Vehicle, 2.0% AXR-270 Cream and Vehicle, and 0.2% AXR-270 Cream and 2.0% AXR-270 Cream will be presented from each model together with two-sided p-values and 95% confidence intervals at each post-baseline visit. The differences between Day 8 and baseline, Day 15 and baseline, and Day 22 and baseline for each treatment individually will also be presented from the model with two-sided p-values and 95% confidence intervals at each post-baseline visit.

Sample SAS longitudinal model code:

```

PROC MIXED DATA=INDATA;
  BY <EYE> <PARAMETER>; ** include <EYE> as applicable;
  CLASS <TREATMENT> <SUBJECT> <VISIT>;
  MODEL <ENDPOINT>=<TREATMENT> <VISIT> <TREATMENT>*<VISIT> <BASELINE>;
  REPEATED <VISIT> / SUBJECT=<SUBJECT> TYPE=UN;
  RANDOM Intercept;
  LSMEANS <TREATMENT>*<VISIT> / CL ALPHA=0.05;
  ESTIMATE '2.0 - Vehicle @ Day 8' <TREATMENT> -1 0 1
           <TREATMENT>*<VISIT> -1 0 0 0 0 0 1 0 0 /

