- Study Eye FCS Superior Zone (2 responder levels)
 - 0 Score
 - 1+ step improvement
- Study Eye FCS Temporal Zone (2 responder levels)
 - 0 Score
 - 1+ step improvement
- Study Eye Bulbar Conjunctival Hyperemia (2 responder levels)
 - 0 Score
 - 1+ step improvement
- OSDI (1 responder level)
 - <13 Score
- Study Eye Unanesthetized Schirmer Test (1 responder level)
 - >14 mm

Improvement as mentioned above means reduction in score.

Time to resolution will be defined as the duration between the date that a subject’s study eye/eyelid or subject, as appropriate per the endpoint (see Section 2.5.1), reaches a predefined “resolution” value post-baseline and the date of the first dose of study drug, i.e., (date of response – date of first dose) + 1. Time to resolution will be summarized by treatment. The differences, 95% CIs, and p-values, assuming equal variance (pooled), from a two-sample t-test will be provided for 0.2% AXR-270 vs Vehicle, 2.0% AXR-270 vs Vehicle, and 2.0% AXR-270 vs 0.2% AXR-270.

Counts and percentages of subjects/eyes that respond will be presented by treatment. P-values from a chi-squared test will be provided for 0.2% AXR-270 vs Vehicle, 2.0% AXR-270 vs Vehicle, and 2.0% AXR-270 vs 0.2% AXR-270.

By subject listings will be provided for each of the efficacy variables.

Change from baseline figures will be presented for the following:

- Eye discomfort VAS
- Eye dryness VAS
- Total MGD Score
- Vascularity of the eyelid margin
- Upper lid LGS
- tFCS
- Bulbar conjunctiva Hyperemia
- OSDI
- Modified BLISS
- Unanesthetized Schirmer Test

Sponsor:	AxeroVision, Inc.		
Protocol:	AXR201901		
Document Version No.:	1.1	Document Date:	26-OCT-2020

- IOP

The mean change from baseline by treatment will be plotted along the y-axis and visit along the x-axis. Standard deviation bars will be presented along with an asterisk (*) above or below the bars to indicate whether there is significance at an $\alpha=0.05$ level for the treatment compared to vehicle.

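### The protocol makes efficacy p-values descriptive, but the SAP turns them into formal 0.05 tests starred for significance on the figures, waives multiplicity and does not list the change

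*SAP*

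**What the plan says.** - **Protocol 9.7**, in full, is one sentence: "P-values will be descriptive in nature". Protocol 3.1.2 calls all efficacy endpoints exploratory, and Protocol 9.6 reports no formal sample size calculation for that reason.
- **SAP 4.2.1:** "Formal statistical hypothesis testing will be performed on the VAS scores, Total MGD score, eyelid margin vascularity, LGS grade", followed by conjunctival hyperemia, Schirmer, TBUT, FCS and OSDI, "with all tests conducted at the 2-sided, 0.05 level of significance".
- **SAP 4.2.5:** "Multiplicity is not of concern for this study".
- **SAP 4.6** repeats that "All efficacy endpoints are exploratory in nature". It then asks for "Least squares means for each treatment group and for the differences between 0.2% AXR-270 Cream and Vehicle, 2.0% AXR-270 Cream and Vehicle", and for the two doses against each other, with two-sided p-values and 95% confidence intervals at each post-baseline visit. For the change-from-baseline figures it says: "Standard deviation bars will be presented along with an asterisk (*) above or below the bars to indicate whether there is significance" at the 0.05 level for each treatment against vehicle.
- **SAP Section 5** lists four additions to the protocol's analyses: responder analysis, time to resolution, the dose-against-dose comparison and within-arm change. A change in the status of the p-values is not among them.

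**The concern.** A decision not to adjust for multiplicity and a decision to declare significance do not belong together. The first is sound while p-values only describe the data; the protocol takes that position. The SAP keeps the waiver but drops the descriptive status.

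The word formal looks deliberate. SAP 4.5 rules out formal comparisons of baseline data, and SAP 4.8.1 rules out formal hypothesis testing of adverse event rates. The SAP therefore separates formal testing from description and puts efficacy on the formal side. SAP 1.1 also says that the document sets out its differences from the protocol, so a reader would expect to find this one in Section 5.

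At stake is how the efficacy output may be described. An asterisk on a figure carries no caveat. With no primary efficacy comparison and no testing order named, any starred visit on any outcome can be reported as a statistically significant effect under the SAP, although the protocol does not allow for such a claim.

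**Working it through.** **1. The plan's own figure.** The SAP states 0.05, two-sided, for each test. For one test 1 − 0.95¹ = 0.05, so the level is correct per comparison. Neither document states a trial-wise error rate, power or effect size, so there is nothing further to reproduce.

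**2. The starred set.** SAP 4.6 lists 11 change-from-baseline figures: eye discomfort VAS, eye dryness VAS, total MGD score, lid margin vascularity, upper lid LGS, tFCS, bulbar hyperemia, OSDI, Modified BLISS, Schirmer and IOP. Two of these have no planned between-arm test. SAP 2.5.1 treats Modified BLISS as categorical and excludes it from the modelled variables. SAP 4.8.4 only summarizes IOP. That leaves 11 − 2 = 9 outcomes with a model test.

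The figures plot visit on the horizontal axis and compare each treatment with vehicle. I read this as one possible asterisk per dose and visit:

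- possible asterisks: 9 outcomes × 2 doses × 3 visits = 54
- expected false asterisks if the product is inactive: 54 × 0.05 = 2.7
- if only Day 22 is counted: 9 × 2 = 18 tests, and 18 × 0.05 = 0.9 expected

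The expected counts do not depend on correlation. They assume that each test has exact 5% size.

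**3. Chance of at least one false asterisk.** This does depend on correlation, which the documents do not give. Both doses are compared with the same pooled vehicle arm (SAP 4.2.3), so the formula 1 − 0.95⁵⁴ = 0.94 for independent tests is too high. I simulated null trials with normal test statistics, three equal arms, a shared vehicle arm and an assumed between-visit correlation of 0.6:

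| Assumed between-endpoint correlation | 0 | 0.4 | 0.6 | 0.9 |
|---|---|---|---|---|
| At least one of 54 asterisks | 0.88 | 0.80 | 0.70 | 0.44 |

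**4. All modelled outcomes at Day 22.** SAP 4.6 gives 2 VAS + MGD + vascularity + TBUT + 3 LGS measures + tFCS + 5 FCS zones + hyperemia + OSDI + Schirmer = 17 outcomes.

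- 17 × 2 doses = 34 tests, and 34 × 0.05 = 1.7 false positives expected
- independent tests would give 1 − 0.95³⁴ = 0.83; with the shared vehicle arm and uncorrelated endpoints the simulation gives about 0.80
- the figure falls to about 0.25 at correlation 0.9

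High correlations are plausible for part of this set, because tFCS is the total of the five zones that are also counted.

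**5. Other p-values.** SAP 4.6 lists 36 responder definitions, each tested for three pairs of arms: 36 × 3 = 108 chi-squared tests, or 108 × 0.05 = 5.4 expected at p < 0.05 under no effect. Time to resolution adds at most the same number. The SAP does not say that every responder level is also a resolution value, so 108 is an upper bound there.

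**The case against.** The other side has a good case on several points.

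- **Per-test level.** The SAP attaches 0.05 to each test. A reader might infer that it presents 5% as the trial's overall false-positive risk and so misstates it. The documents do not support that, because no trial-wise rate is claimed anywhere.
- **Exploratory setting.** The primary objective is safety and tolerability, and no efficacy success criterion depends on these p-values. A reader might infer that the absence of adjustment is itself an error. It is not: unadjusted testing is an accepted choice in an exploratory trial, and SAP 4.6 restates the exploratory status in the same section as the asterisk rule.
- **Section 5.** Protocol 9.4 already plans a longitudinal model and Protocol 9.7 already expects p-values. What changed is their status, not the analysis, and Section 5 lists analyses. This softens the omission, but the status change is still recorded nowhere.
- **Size.** The 34-test family is not what gets starred: TBUT and the five FCS zones have no figure. The within-arm tests do not belong in a count of false positives from an inactive product either, since subjects are selected for severity at baseline and may change without any drug effect.

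These arguments limit the point to the conflict in labelling and put its size on the 54 asterisks. They do not remove the conflict. Calling the endpoints exploratory does not reconcile formal tests and starred significance with p-values that the protocol calls descriptive.

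**Conclusion.** The point stands as an unreconciled conflict between the protocol and the SAP: significance is to be declared on efficacy comparisons for which the protocol allows only descriptive p-values, with error control expressly waived and the change unlisted. The per-test level and the choice not to adjust are both acceptable in themselves.

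On the starred set, 2.7 false asterisks are expected from an inactive product, and at least one is more likely than not unless the endpoints are very highly correlated. The expected count rests on exact 5% tests and one asterisk per dose and visit. The probabilities also rest on the assumed correlations and the normal approximation.

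The asterisk rule also covers Modified BLISS and IOP, where it cannot be applied as written because no between-arm test is specified.

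Severity is minor to moderate. No model, estimate, interval or p-value is wrong on this account. What is affected is the claim that may be attached to them.

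**What to change.** Before unmasking, amend the SAP as follows:

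- **4.2.1:** replace the sentence on formal testing at 0.05 with a statement that nominal two-sided p-values and 95% confidence intervals will be given, unadjusted and for description only, in line with Protocol 9.7.
- **4.2.5:** state that no multiplicity adjustment is made and that no efficacy result will be called statistically significant.
- **4.6:** remove the asterisks, or footnote them as nominal p < 0.05, unadjusted and descriptive. Drop them in either case for Modified BLISS and IOP.
- **If a formal claim is wanted:** name one endpoint, one visit and one contrast before unmasking, and list the change in Section 5.

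The cost is SAP wording and a figure template, with no new data and no change in conduct. The downside is that no efficacy result can be headlined as statistically significant, unless the single pre-specified comparison is adopted.

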4.2.2. Computing Environment

All descriptive statistical analyses will be performed using SAS statistical software (Version 9.4), unless otherwise noted. Medical History and adverse events will be coding using Medical Dictionary for Regulatory Activities (MedDRA) version 23.0 – updated Apr2020. Concomitant medications will be coded using B3 World Health Organization (WHO) Drug Global – March 2020.

4.2.3. Methods of Pooling Data

Vehicle from Cohort 1 and Cohort 2 will be pooled for analysis.

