2. STUDY DESIGN

2.1. Synopsis of Study Design

This is a multi-center, double-masked, randomized, vehicle-controlled, two cohort study. Approximately 126 subjects with a diagnosis of symptomatic posterior blepharitis associated with MGD will be enrolled in the trial. Subjects will be randomized into one of the three treatments below.

- 0.2% AXR-270 Cream (approximately 42 subjects in Cohort 1)
- 2.0% AXR-270 Cream (approximately 42 subjects in Cohort 2)
- Vehicle (approximately 42 subjects, 21 in Cohort 1 and 21 in Cohort 2)

Randomly assigned treatments will be administered in both eyes.

[figure not shown]
In Cohort 1, approximately 63 subjects with a diagnosis of symptomatic posterior blepharitis associated with MGD meeting all inclusion/exclusion criteria at the Screen visit (Visit 1) will be asked to discontinue their eyelid hygiene regimen and use only Sponsor supplied commercial sterile eyelid wipes between Visit 1 and Visit 2 daily (Equalization Period). Subjects will then be evaluated at Baseline/Randomization visit (Visit 2; Week 0/Day 1) to confirm that they meet all inclusion/exclusion criteria and are eligible for 2:1 randomization to 0.2% AXR-270 Cream or its Vehicle. Subjects will receive in-clinic dose administration and then supplied with sufficient IP to apply once daily (QD) at home in the evening during the treatment period. Subjects will self-administer IP QD (approximately 50 mg per eyelid) in the evenings beginning on Day 2. Subjects will return for assessments on Visit 3 (Week 1/Day 8), Visit 4 (Week 2/Day 15), and Visit 5 (Week 3/Day 22).

Following the completion of the 15th subject from Visit 4 of Cohort 1, the Data Safety Review Committee (DSRC) will meet to review safety data and will make a recommendation on whether to escalate to a higher 2.0% dose of AXR-270 Cream for Cohort 2, which if recommended, will begin immediately upon completion of enrollment in Cohort 1.

In Cohort 2, approximately 63 subjects will be randomized 2:1 to 2.0% AXR-270 Cream or its Vehicle. Cohort 2 will follow the same visit schedule as Cohort 1.

Sponsor:	AxeroVision, Inc.		
Protocol:	AXR201901		
Document Version No.:	1.1	Document Date:	26-OCT-2020

Figure 1 Study Schematic (Cohort 1)

Note: Cohort 2 (AXR-270 2.0% Cream or vehicle) follows the same visit schedule as above and will start enrolling once enrollment of Cohort 1 is complete.

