4.2.4. Adjustments for Covariates

No formal statistical analysis that adjusts for possible covariate effects is planned.

Sponsor:	AxeroVision, Inc.		
Protocol:	AXR201901		
Document Version No.:	1.1	Document Date:	26-OCT-2020

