5. CHANGES TO PLANNED ANALYSES

The following analyses are provided in the SAP but not planned in the protocol:

- Responder analysis in Section 4.6
- Time to resolution analysis in Section 4.6
- Additional evaluation of the difference between 2.0% AXR-270 Cream and 0.2% AXR-270 Cream at each post-baseline visit
- Additional evaluation of the within treatment change-from-baseline difference at each post-baseline visit

Sponsor:	AxeroVision, Inc.		
Protocol:	AXR201901		
Document Version No.:	1.1	Document Date:	26-OCT-2020

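### The dose-versus-dose contrast is tested as if randomised although dose and cohort coincide, and no cohort-adjusted result accompanies the pooled-vehicle analysis

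*SAP*

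**What the plan says.** SAP 2.1 plans about 42 subjects on 0.2% and 21 on vehicle in Cohort 1, and about 42 on 2.0% and 21 on vehicle in Cohort 2. Cohort 1 subjects are "eligible for 2:1 randomization to 0.2% AXR-270 Cream or its Vehicle"; Cohort 2 uses the same ratio with the higher strength and "will start enrolling once enrollment of Cohort 1 is complete". Protocol 5.1.2 makes cohort an input to the IWRS, so allocation is made within cohort.

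On analysis:

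- SAP 4.2.3: "Vehicle from Cohort 1 and Cohort 2 will be pooled for analysis".
- SAP 4.2.4: "No formal statistical analysis that adjusts for possible covariate effects is planned". The model in 4.6 does carry baseline, so this sentence cannot be taken literally, but cohort appears nowhere.
- SAP 4.6, sample code: "MODEL <ENDPOINT>=<TREATMENT> <VISIT> <TREATMENT>*<VISIT> <BASELINE>".
- SAP 4.6, longitudinal model: differences, p-values and 95% confidence intervals at each post-baseline visit for both doses against Vehicle and for the two doses against each other. Time to resolution has the same three comparisons by t-test. For responders: "P-values from a chi-squared test will be provided for 0.2% AXR-270 vs Vehicle, 2.0% AXR-270 vs Vehicle, and 2.0% AXR-270 vs 0.2% AXR-270".
- SAP 5 lists as an addition to the protocol: "Additional evaluation of the difference between 2.0% AXR-270 Cream and 0.2% AXR-270 Cream at each post-baseline visit". It does not say that this comparison is non-randomised.
- SAP 4.2.6 plans no subgroups, and no table in SAP 7.1 is by cohort.

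On the status of the p-values, Protocol 9.7 treats them as descriptive. SAP 4.2.1 says "Formal statistical hypothesis testing will be performed on the VAS scores" and other endpoints, two-sided at 0.05.

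**The concern.** No subject can be allocated to 0.2% rather than 2.0% by chance; the dose follows from the date of enrolment. Among the active arms, dose and cohort are the same variable, so the direct contrast cannot tell a dose effect from a change over time. SAP 2.2 describes randomisation to one of three treatments. It prints the cohort beside each dose but does not draw this consequence.

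Pooling vehicle brings a weaker form of the problem into each dose-versus-Vehicle comparison, because half the controls come from the other cohort.

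A shift between cohorts is plausible. Recruitment is sequential across 10 to 16 sites, so site mix and season can differ. Staff enter the cohort in the IWRS and so know which active strength is possible, which can affect expectation for symptoms and investigator-rated signs. Adjustment for baseline can remove a shift that acts through baseline severity. It cannot remove a change in vehicle response or in how raters grade.

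No confirmatory decision is at stake. What is at stake is the reading of estimates, intervals, p-values and figure asterisks. A shift toward improvement in Cohort 2 flatters 2.0%, penalises 0.2%, and can look like a dose response.

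**Working it through.** **Inputs.** From SAP 2.1: cells of 42 (0.2%), 21 (Cohort 1 vehicle), 42 (2.0%) and 21 (Cohort 2 vehicle). From SAP 4.2.1: two-sided 0.05. No SD, effect size or cohort shift is given, so results are in SD units of the change score. The additive shift d (positive = more improvement in Cohort 2) is assumed to lie between 0 and 0.5 SD. The calculation uses one time point and ignores baseline adjustment, repeated measures and dropout.

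**The plan's own figures.** 63 × 2/3 = 42 and 63 × 1/3 = 21; 2 × 63 = 126; pooled vehicle 21 + 21 = 42. All reproduce. The non-concurrent share of each dose's controls is 21/42 = 50%.

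**Identifiability.** With only the two active arms, a design matrix of intercept, dose and cohort has rank 2 of 3. Dose and cohort cannot be separated. Adding the vehicle arms gives 4 parameters for 4 cells, so a cohort term can then be estimated.

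**Bias of the planned contrasts.** The pooled vehicle mean moves by (21 × 0 + 21 × d)/42 = d/2. Hence:

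- 2.0% versus Vehicle: d − d/2 = +d/2
- 0.2% versus Vehicle: 0 − d/2 = −d/2
- 2.0% versus 0.2%: d − 0 = d

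**Standard errors.**

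- Planned, all three contrasts: √(1/42 + 1/42) = 0.218
- Dose versus own-cohort vehicle: √(1/42 + 1/21) = 0.267, ratio 1.22
- Difference of the two within-cohort effects: √(2/42 + 2/21) = 0.378, ratio 1.73

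**Rejection with no drug effect.** For bias b: Φ(−1.96 − b/SE) + 1 − Φ(1.96 − b/SE), SE = 0.218.

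| d (SD) | Each dose v Vehicle (b = d/2 in size) | 2.0% v 0.2% (b = d) |
|---|---|---|
| 0 | 5.0% | 5.0% |
| 0.1 | 5.6% | 7.4% |
| 0.2 | 7.4% | 15.0% |
| 0.3 | 10.6% | 28.0% |
| 0.5 | 20.9% | 63.0% |

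Simulated t-tests (20,000 trials per value) at d = 0, 0.2, 0.3 and 0.5 gave 4.9, 7.0, 10.0 and 19.5% for 2.0% versus pooled vehicle, and 4.6, 15.0, 27.6 and 62.0% for dose versus dose. At d = 0.3 the errors are lopsided: false benefit is 10.2% for 2.0% and 0.4% for 0.2%, while false inferiority of 0.2% is 10.2%.

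**Bias against precision.** Mean squared error, planned versus cohort-adjusted:

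- Dose versus Vehicle: 0.0476 + d²/4 against 0.0714
- Dose versus dose: 0.0476 + d² against 0.1429

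Both cross at d² = 0.0952, d = 0.31 SD. Below that the planned contrasts do better; above it they do worse. At d = 0.5 the figures are 0.110 against 0.071, and 0.298 against 0.143.

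**Can the vehicle data settle it?** Cohort 1 versus Cohort 2 vehicle has SE √(2/21) = 0.309 and a 95% half-width (t, 40 df) of 0.62 SD. Power to detect d = 0.2, 0.3 or 0.5 is 10, 16 or 37%. A non-significant difference would therefore say little.

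**The case against.** The strongest reply is that little hangs on this. The primary objective is safety and tolerability, efficacy is exploratory, no sample size was calculated, and escalation rests on the DSRC's safety review. That limits the severity and is accepted. It does not remove the point, because bias affects the estimate and interval as well as the p-value, and the SAP does plan formal testing at 0.05.

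Second, pooling has good support. There is one vehicle formula, with common eligibility, visit schedule and equalization period, and baseline is in the model. Cohort 2 opens directly when Cohort 1 enrolment closes, so follow-up can overlap. The planned contrasts also have lower mean squared error over most of the assumed range of d. This stands, and is why pooling may remain the lead. It does not help the direct dose contrast, in which no vehicle data offset a shift.

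Third, d is assumed and the figures are not from the planned longitudinal model; adjustment and repeated measures could move them either way. This stands too. The 63% is the extreme of the range for one contrast, and the figure asterisks, which concern treatment against vehicle, carry only the d/2 bias. That a cohort term restores the 5% level follows from assuming an additive shift; it is not evidence that the shift is additive.

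Fourth, within-cohort responder tests will be sparse. With 21 vehicle subjects, an expected count falls below 5 when overall response is under 5/21 = 24%, and LGS is done at a subset of sites only. This affects how the fix is carried out, not whether it is needed.

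**Conclusion.** The point holds and should be fixed. The dose comparison is non-randomised and fully confounded with cohort, yet it gets p-values in three analyses without a caveat. Half of each dose's controls are non-concurrent, and nothing planned would show whether that matters.

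The bias fractions (d/2, d/2 and d) follow from the planned allocation and an additive shift. The error rates also depend on d, which the documents do not give: roughly 7 to 21% for dose versus Vehicle and 15 to 63% for dose versus dose, for d between 0.2 and 0.5 SD. If d is zero, the planned analysis is unbiased and the more precise choice. The defect is the missing companion result and label, not pooling itself.

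**What to change.** 1. Keep the pooled-vehicle analysis as the lead for each dose versus Vehicle. Prespecify beside it the same longitudinal model with cohort and cohort-by-visit terms, so that each dose is compared with its own cohort's vehicle. For time to resolution and responders, make the same comparisons within cohort, with an exact test where expected counts are below 5.
2. Add a descriptive table of Cohort 1 vehicle against Cohort 2 vehicle. State that a non-significant difference does not justify pooling.
3. For 2.0% versus 0.2%, drop the p-value from the raw contrast and label it non-randomised. Report instead (2.0% minus Cohort 2 vehicle) minus (0.2% minus Cohort 1 vehicle), noting that it is indirect and assumes an additive cohort shift.

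**Cost.** No new data are needed, since cohort is already recorded in the IWRS. SAP 7.1 lists eleven continuous efficacy table families. If workload matters, the companion results can be confined to the endpoints marked there as topline.

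The price in precision falls on the companion results:

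- Dose versus Vehicle: SE rises from 0.218 to 0.267 SD, and power at an assumed 0.5 SD effect falls from 63% to 46%.
- Dose versus dose: SE rises from 0.218 to 0.378 SD and power falls from 63% to 26%. The difference detectable with 80% power is (1.96 + 0.84) × 0.378 = 1.06 SD, so this result should be presented as imprecise.
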